7 ANALYSIS SETS AND SUBGROUPS

7.1 Analysis sets

The following analysis sets are defined:

Population	Description
Screened	The screened analysis set is defined as all patients who sign the informed consent form (ICF).
Intent-to-Treat (ITT)	Part 1: The ITT set is defined as all patients to whom IMP is assigned. Part 2: The ITT set is defined as all patients who are randomized to the IMP.
Modified Intent-to-Treat (mITT)	Part 1: The mITT set is defined as all patients to whom IMP is assigned and have a baseline and at least one post-baseline (i.e., one on-treatment or post-treatment) tumor assessment (clinical or imaging assessment). Part 2: The mITT set is defined as all patients who are randomized to the IMP and have a baseline and at least one post-baseline (i.e., one on-treatment or post-treatment) tumor assessment (clinical or imaging assessment).
Safety (SAF)	The safety set is defined as all patients who have received IMP (i.e., at least 1 dose of W_pro1 and/or cemiplimab).
DLT Evaluation	Only applicable for Part 1: The DLT evaluation set includes all patients from the safety set who either have completed the DLT evaluation period and meet the minimum exposure criterion or have experienced a DLT during C1. Patients who do not experience any DLTs during C1 are considered to be evaluable if they have been observed for a minimum of 21 days following the first dose and are considered to have sufficient safety data to conclude that a DLT did not occur. A patient is considered to have met the minimum exposure criterion if the relative dose intensity of W_pro1 in C1 is at least 90%.
Per Protocol (PP)	The per protocol (PP) set is defined as all patients who have received IMP and fulfil the following criteria: 
 • The absence of any important protocol deviations that could affect the primary efficacy analysis • The completion of a minimal exposure to the treatment of 1 cycle • Availability of baseline and at least one on-treatment / post-treatment tumor assessment Important deviations will lead to an exclusion of patients from the PP set and will be agreed at the data review meeting (DRM) prior to database snapshot for the final analysis. Protocol deviations that may be considered important will be specified in the SAP (see Section 7.2)

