Pharmacodynamic	The pharmacodynamic set is defined as all patients who have received IMP (i.e., at least 1 dose of W_pro1 and/or cemiplimab) and with a baseline and at least 1 on-treatment/post-treatment follow-up

Population	Description
	pharmacodynamic assessment as specified in Section 8.8.1 (i.e. Hormones (Testosterone), Cytokines).
Subsequent Cemiplimab Monotherapy on Progression (Cemi Mono on PD)	Only applicable for Part 2 Arm 1B: The subsequent cemiplimab monotherapy on progression set (Cemi Mono on PD) is defined as all mCRPC patients in Arm 1B (W_pro1 monotherapy) who switch to cemiplimab monotherapy after disease progression and who received at least one dose of cemiplimab.

The DLT evaluation set will be used for the evaluation of DLTs in order to assess the REDR in Part 1 of the trial.

The safety set will be used for all other safety analyses, while the mITT set will be used as primary analysis set for efficacy analyses.

The subsequent cemiplimab monotherapy on progression set will be used for all exploratory safety and efficacy analyses for the Arm 1B patients who received cemiplimab (i.e., at least 1 dose of cemiplimab) after progression to W_pro1 monotherapy.

The ITT analysis set will be used for disposition analyses.

Further, the ITT and PP sets will be used for sensitivity analyses of some predefined efficacy endpoints depending on the number of patients excluded. If none of the patients are excluded from the mITT set, compared to the ITT set, or if the number of patients excluded from the PP set is small (exclusion rate $\leq 10\%$), no additional sensitivity analyses for the ITT or the PP set will be generated. The final decision to perform sensitivity analyses for the ITT set or for the PP set will be made during the DRM meeting for the final analysis.

All safety analyses and analyses based on the Pharmacodynamic set will be based on the treatment actually taken by the patient (“as treated”).

All other analyses will be based on the treatment the patient was assigned/randomized to (“as randomized”), unless stated otherwise.

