8.7.4 Exploratory analyses

Exploratory efficacy analyses will be performed using the mITT set.

Exploratory efficacy endpoints comprise ORR (in the mCRPC arms and only per iRECIST), DoR, PFS, and OS. Tumor assessments will be performed using PCWG3 for all patient in Part 1 and Part 2 of the trial. For mCRPC patients enrolled in Part 1 and Part 2, tumor assessment using iRECIST (central reading) will be performed in addition.

For mCRPC patients enrolled in Part 1 and Part 2, ORR, DoR, and PFS will be analyzed separately for PCWG3 and iRECIST (central reading).

ORR, and DoR will be analyzed for Part 1 and Part 2 Arms 1A and 1B only.

Sensitivity analyses for exploratory endpoints will be performed using the ITT set and the PP set depending on the number of patients excluded.

In addition, subgroup analyses for some of the exploratory endpoints (i.e. DoR and PFS) will be performed based on the mITT set. The final decision will be made during the DRM.

Exploratory efficacy analyses will also be performed on patients in Arm 1B who are treated with cemiplimab monotherapy following progression after W_pro1 monotherapy. These exploratory analyses will comprise ORR, DoR, PFS (per PCWG3 and iRECIST (central reading)) on cemiplimab monotherapy based on last tumor assessment prior to start of cemiplimab treatment and OS. PFS2 will be analyzed as well. These exploratory efficacy

analyses will be performed using the subsequent cemiplimab monotherapy on progression set.

Exploratory immunogenicity analyses of W_pro1 antigen-specific T-cells based on ELISPOT and further immune monitoring data are not part of this SAP. Respective data will be provided by a central laboratory.

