response (CR or PR) + 1) / 30.4375 in case of censoring.

DoR based on iRECIST (central reading):

OR is defined as iCR or iPR. Disease progression is defined as tumor response =
Confirmed progressive disease (iCPD)

DoR expressed in months for patients whose objective response was confirmed iCR or
iPR = (MIN [Date of first documented disease progression (iCPD), date of death from any
cause] – Date of first documented overall response (iCR or iPR) + 1) / 30.4375 for events

or

(Date of the last evaluable response assessment – Date of first documented overall
response (iCR or iPR) + 1) / 30.4375 in case of censoring.

Progression-free survival

PFS will be analyzed for Part 1 and Part 2 Arms 1A and 1B, Arm 2 and Arm 3.

PFS is defined as the time from the date of the first dose of IMP to the date of the first
disease progression, or death from any cause, whichever occurs first.

Only death dates reported prior to or at the date of trial discontinuation will be considered
in the PFS analysis.

PFS will be analyzed using the Kaplan-Meier method. Kaplan-Meier plots will be
generated.

Patients alive and without disease progression at the data cut-off date or patients lost to
follow-up will be censored at the day of their last response assessment.

Only response assessments prior to or at the start date of the first subsequent anti-cancer
therapy will be considered for PFS analysis. PD within 14 days after the start date of the
first subsequent anti-cancer therapy will be considered.

If no post-baseline tumor response is available, the patient will be censored at the date of
the first dose of IMP.

PFS expressed in months = (MIN [Date of first disease progression, date of death from
any cause] – date of first dose of IMP + 1) / 30.4375 if the patient has a PFS event

or

(Date of last evaluable response assessment – date of first dose of IMP + 1) / 30.4375 in
case of censoring.

In the case that date of the first dose of IMP is missing, randomization date will be used for the calculation of PFS.

For Part 1 and Part 2 Arms 1A and 1B, PFS will be analyzed separately based on PCWG3 and iRECIST (central reading).

Sensitivity analyses of PFS will be performed using the ITT set and the PP set depending on the number of patients excluded.

Overall survival

OS will be analyzed for Part 1 and Part 2 Arms 1A and 1B, Arm 2 and Arm 3.

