OS is defined as the time from the date of the first dose of IMP to the date of death from any cause. OS will be analyzed using the Kaplan-Meier method. Kaplan-Meier plots will be generated.

In case date of death is reported after trial discontinuation date, this data will not be considered in the OS and the patient will be censored at the day of their last date known to be alive.

Patients alive or patients lost to follow-up at the date of analysis cut-off will be censored at the day of their last date known to be alive.

OS expressed in months = (Date of death from any cause – date of first dose of IMP + 1) / 30.4375 for patients with available death date

or

(Last date of known to be alive – date of first dose of IMP + 1) / 30.4375 in case of censoring.

In the case that date of the first dose of IMP is missing, randomization date will be used for the calculation of OS.

8.7.4.2 Exploratory efficacy endpoints for patients in Arm 1B who are treated with cemiplimab monotherapy following progression on W_pro1

Patients in Arm 1B will be given the option to be treated with cemiplimab monotherapy following progression on W_pro1 monotherapy treatment and will be assessed for some exploratory efficacy endpoints, where the last measurement prior to start of cemiplimab treatment will serve as baseline measurement and the time-to-event endpoints (DoR, and PFS) will start from first dose of cemiplimab treatment. In particular, the last radiographic tumor assessment prior to cemiplimab treatment will re-define target and non-target lesions as basis for tumor response assessment on cemiplimab treatment. Additionally, PFS2 will be evaluated based on initial start of IMP.

These exploratory efficacy analyses will be performed using the subsequent cemiplimab monotherapy on progression set.

Objective Response Rate based on PCWG3 and iRECIST (central reading)

ORR will be analyzed separately for PCWG3 and iRECIST (central reading).

The ORR is defined as the number of patients with CR or PR as best objective response per PCWG3 (or number of patients with iCR or iPR as best objective response per iRECIST (central reading)) after start of cemiplimab treatment, divided by the number of patients in the subsequent cemiplimab monotherapy on progression set.

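### OS and PFS are analysed mainly on the mITT set, so a patient who dies before any post-baseline tumor assessment is recorded drops out of the main survival curves

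*SAP*

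**What the plan says.** SAP 8.7.4 lists the endpoints concerned: "Exploratory efficacy endpoints comprise ORR (in the mCRPC arms and only per iRECIST), DoR, PFS, and OS". It assigns them to one set: "Exploratory efficacy analyses will be performed using the mITT set". Protocol 9.4.4 has the same rule.

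SAP 7.1 defines that set for Part 2 as randomized patients who "have a baseline and at least one post-baseline (i.e., one on-treatment or post-treatment) tumor assessment". The parenthesis that follows admits a clinical as well as an imaging assessment. Part 1 has the same requirement with assignment in place of randomization.

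Both clocks start at first dose. SAP 8.7.4.1 says "OS is defined as the time from the date of the first dose of IMP to the date of death from any cause", and the PFS event is "disease progression, or death from any cause, whichever occurs first". The same section censors at first dose any patient with no post-baseline tumor response.

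On wider sets, SAP 7.1 says "the ITT and PP sets will be used for sensitivity analyses of some predefined efficacy endpoints depending on the number of patients excluded". The ITT run is omitted if mITT excludes nobody from ITT; otherwise the data review meeting decides. In SAP 11.1.1 the ITT tables for PFS (under 14.2.3.4 and 14.2.3.5) and OS (under 14.2.3.6) are marked optional.

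**The concern.** Membership of the analysis set is settled after time zero. Someone who dies before a qualifying assessment had an OS event and a PFS event, but appears in neither main curve. The exclusion can only remove early events, so it moves the estimates one way, upwards. This differs from the question of who belongs in the ORR denominator, because here the events themselves disappear.

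The figures exposed are the survival rates that SAP 8.1 reports at 3, 6 and 12 months, and the medians. SAP section 3 says the results might enter a regulatory submission, so readers may take the curves at face value.

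**Working it through.** **1. The plan's own figures.** No sample size, event count or power is stated for OS or PFS. The only sized endpoint is ORR (SAP section 6). Its two-stage design (20, then 33 patients; continue with 2 or more responses; reject at 5 or more) reproduces: power 80.2% at a 20% response rate, and attained type I error 2.18%, inside the nominal 2.5%. Nothing below touches that test.

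**2. Effect of the entry rule.** Let q be the fraction who die before a qualifying assessment and t0 the time of that assessment. For t at or after t0,

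S_mITT(t) = S_ITT(t) / (1 − q), an overstatement of S_ITT(t) × q / (1 − q).

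This needs no survival model. If true 3-month OS is 90% in 33 patients, removing 1, 2 or 3 early deaths gives 0.90/(32/33) = 92.8%, 0.90/(31/33) = 95.8% or 0.90/(30/33) = 99.0%.

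**3. Sizing q in mCRPC.** Inputs:
- First scheduled post-baseline scan at C3D15 (Protocol 8.1.1.1): day 2 × 21 + 15 = 57, so t0 = 56/30.4375 = 1.84 months.
- Background median OS in mCRPC, m = 16 to 34 months (Protocol 2.1.1).
- Assumptions not in the documents: exponential survival, and no clinical assessment recorded before the scan.

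q = 1 − exp(−ln 2 × t0 / m)

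| | m = 16 months | m = 34 months |
|---|---|---|
| q | 7.7% | 3.7% |
| Patients removed, of 20 | 1.5 | 0.7 |
| Patients removed, of 33 | 2.5 | 1.2 |
| 3-month OS, ITT / mITT | 87.8% / 95.1% | 94.1% / 97.7% |
| 6-month OS, ITT / mITT | 77.1% / 83.5% | 88.5% / 91.9% |
| 12-month OS, ITT / mITT | 59.5% / 64.4% | 78.3% / 81.3% |
| Overstatement at 3 months | 7.3 points | 3.6 points |
| Overstatement at 12 months | 4.9 points | 3.0 points |

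**4. Sensitivity to the scan window.** With the ±7 days (day 50 to 64), q runs from 6.7% to 8.6% at m = 16 and from 3.2% to 4.1% at m = 34. A scan at day 64 raises the 3-month ceilings to 0.878 × 0.0858/0.9142 = 8.2 points and 0.941 × 0.0413/0.9587 = 4.1 points. PFS estimates after the first assessment carry the same factor 1/(1 − q), about 1.03 to 1.09.

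**5. Lower end.** If every early death was preceded by a recorded clinical assessment, q = 0 and the two sets agree.

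**6. Does moving to ITT repair PFS?** Not alone. Under the SAP 8.7.4.1 rule, read literally, a patient who dies with no post-baseline tumor response is censored at first dose. He then adds nothing to the curve after time zero, so the ITT estimate equals the mITT one. OS has no such rule.

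**7. LPC.** The only scheduled post-baseline imaging is at the end of C8/EoT (C8D1 is day 148), so the selection window can be longer. The documents give no early death rate there, so it is not sized.

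**The case against.** Several points on the other side stand.

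- **The scan is not the gate.** A clinical assessment also qualifies. Patients attend on days 1, 8 and 15 of cycles 1 and 2, clinical progression has its own CRF page (SAP 8.2), and the schedule allows tumor assessment at unscheduled visits. A reader might infer that every patient who dies before week 8 is lost; the documents do not support that. Only those with no qualifying record are. The loss remains possible, because routine tumor response assessment is not scheduled before C3D15 and the set definition does not say which records count as a clinical assessment.
- **ITT analyses are foreseen.** They are omitted automatically only when nobody is excluded, which is when the bias is zero. The 10% tolerance concerns the PP set. What remains is that the data review meeting has the final say in an open-label trial that has already had an interim analysis.
- **Early deaths stay visible.** The PFS and OS listings (16.2.6.4.3 to 16.2.6.4.5) are on ITT, deaths are listed on the safety set, and exclusions are tabulated with reasons (SAP 8.5). The loss is from the curves and estimates, not from the report.
- **The inputs are soft.** The median OS range is background for mCRPC generally, not for this pre-treated population. Protocol 2.1.1 also gives the same 16 to 34 months for time to castration resistance, which casts some doubt on the figure.
- **Between-arm results.** A reader might infer that the Arm 1A versus 1B log-rank and Cox results are biased. Both arms share the entry rule and visit schedule; material distortion would need unequal exclusions, and nothing in the documents shows that. These comparisons are declared purely exploratory.

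**Conclusion.** The point holds in a limited form. As written, the plan can remove early deaths from the main OS and PFS curves, and the remedy it contains is optional. The direction is certain whenever such a patient exists; the number of such patients is unknown. For mCRPC with a first scan at day 57, the ceiling is 7.7% to 3.7% of patients, worth about 7.3 to 3.6 points on 3-month OS and 4.9 to 3.0 points on 12-month OS. This rests on exponential survival, the protocol's background median and no earlier clinical assessment. The floor is zero.

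The ORR hypothesis test is not touched by this point. Nor are the analyses of Arm 1B patients who switch to cemiplimab, which use their own analysis set. OS and PFS are exploratory, so this concerns descriptive accuracy, not the trial's one formal decision.

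**What to change.** 1. In SAP 8.7.4 and Tables 14.2.3.4.x, 14.2.3.5.x and 14.2.3.6.x, make ITT (as randomized) the main set for OS and PFS, remove the optional label from those tables, and keep mITT as a sensitivity analysis. ITT is preferable to the safety set, which is analysed as treated. The SAP already substitutes the randomization date when the first-dose date is missing, so both endpoints can be computed on ITT.
2. In SAP 8.7.4.1, state that a death before any post-baseline assessment is a PFS event at the date of death. Restrict censoring at first dose to patients alive without a post-baseline assessment.
3. Record the change from Protocol 9.3 and 9.4.4 in SAP Appendix 1, which lists changes to the protocol-planned analyses.

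The cost is SAP wording and a documented departure from the protocol's analysis set. The ITT tables are already listed. The estimates may become slightly less favourable.

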8.7.4.1 Exploratory efficacy endpoints

Objective Response Rate based on iRECIST (central reading)

ORR based on iRECIST will be analyzed for mCRPC patients in Part 1 and Part 2 only.

The ORR is defined as the number of patients with iCR or iPR as best objective response per iRECIST divided by the number of patients in the mITT set. Patients not meeting the criteria for iCR or iPR, including those without any post-baseline tumor assessments, will be considered as non-responders. The ORR will be summarized with absolute and relative frequencies along with two-sided 95% Clopper-Pearson CIs by treatment group.

BOR (all categories) will be summarized with absolute and relative frequencies.

Tumor response assessment including overall response and BOR will be listed. In addition, listings including all tumor assessments per iRECIST (central reading) (target lesion, non-target lesion, new lesion) will be generated.

Duration of Response

DoR will be analyzed for Part 1 and Part 2 Arms 1A and 1B only. DoR will be analyzed separately for PCWG3 and iRECIST (central reading).

The DoR is defined as the time from the date of first radiographic documented OR to the date of first disease progression or death from any cause, whichever occurs first. Only patients who experience a confirmed OR will be analyzed for DoR.

In case death date is reported after trial discontinuation date, these death details will not be considered in the DoR analysis. The patient will be censored at the day of the last response assessment.

DoR will be analyzed using the Kaplan-Meier method. Kaplan-Meier plots will be generated.

Patients alive and without disease progression at data cut-off date or patients lost to follow-up will be censored at the day of their last response assessment.

Only response assessments prior to or at the start date of the first subsequent anti-cancer therapy will be considered for DoR analysis. PD within 14 days after the start date of the first subsequent anti-cancer therapy will be considered.

DoR based on PCWG3:

OR is defined as CR or PR. Disease progression is defined as tumor response = Progressive Disease (PD)

DoR expressed in months for patients whose objective response was confirmed CR or PR
= (MIN [Date of first documented disease progression (PD), date of death from any cause]
– Date of first documented overall response (CR or PR) + 1) / 30.4375 for events

or

(Date of the last evaluable response assessment – Date of first documented overall
response (CR or PR) + 1) / 30.4375 in case of censoring.

DoR based on iRECIST (central reading):

OR is defined as iCR or iPR. Disease progression is defined as tumor response =
Confirmed progressive disease (iCPD)

DoR expressed in months for patients whose objective response was confirmed iCR or
iPR = (MIN [Date of first documented disease progression (iCPD), date of death from any
cause] – Date of first documented overall response (iCR or iPR) + 1) / 30.4375 for events

or

(Date of the last evaluable response assessment – Date of first documented overall
response (iCR or iPR) + 1) / 30.4375 in case of censoring.

Progression-free survival

PFS will be analyzed for Part 1 and Part 2 Arms 1A and 1B, Arm 2 and Arm 3.

PFS is defined as the time from the date of the first dose of IMP to the date of the first
disease progression, or death from any cause, whichever occurs first.

Only death dates reported prior to or at the date of trial discontinuation will be considered
in the PFS analysis.

PFS will be analyzed using the Kaplan-Meier method. Kaplan-Meier plots will be
generated.

Patients alive and without disease progression at the data cut-off date or patients lost to
follow-up will be censored at the day of their last response assessment.

Only response assessments prior to or at the start date of the first subsequent anti-cancer
therapy will be considered for PFS analysis. PD within 14 days after the start date of the
first subsequent anti-cancer therapy will be considered.

If no post-baseline tumor response is available, the patient will be censored at the date of
the first dose of IMP.

PFS expressed in months = (MIN [Date of first disease progression, date of death from
any cause] – date of first dose of IMP + 1) / 30.4375 if the patient has a PFS event

or

(Date of last evaluable response assessment – date of first dose of IMP + 1) / 30.4375 in
case of censoring.

In the case that date of the first dose of IMP is missing, randomization date will be used for the calculation of PFS.

For Part 1 and Part 2 Arms 1A and 1B, PFS will be analyzed separately based on PCWG3 and iRECIST (central reading).

Sensitivity analyses of PFS will be performed using the ITT set and the PP set depending on the number of patients excluded.

Overall survival

OS will be analyzed for Part 1 and Part 2 Arms 1A and 1B, Arm 2 and Arm 3.

OS is defined as the time from the date of the first dose of IMP to the date of death from any cause. OS will be analyzed using the Kaplan-Meier method. Kaplan-Meier plots will be generated.

In case date of death is reported after trial discontinuation date, this data will not be considered in the OS and the patient will be censored at the day of their last date known to be alive.

Patients alive or patients lost to follow-up at the date of analysis cut-off will be censored at the day of their last date known to be alive.

OS expressed in months = (Date of death from any cause – date of first dose of IMP + 1) / 30.4375 for patients with available death date

or

(Last date of known to be alive – date of first dose of IMP + 1) / 30.4375 in case of censoring.

In the case that date of the first dose of IMP is missing, randomization date will be used for the calculation of OS.

8.7.4.2 Exploratory efficacy endpoints for patients in Arm 1B who are treated with cemiplimab monotherapy following progression on W_pro1

Patients in Arm 1B will be given the option to be treated with cemiplimab monotherapy following progression on W_pro1 monotherapy treatment and will be assessed for some exploratory efficacy endpoints, where the last measurement prior to start of cemiplimab treatment will serve as baseline measurement and the time-to-event endpoints (DoR, and PFS) will start from first dose of cemiplimab treatment. In particular, the last radiographic tumor assessment prior to cemiplimab treatment will re-define target and non-target lesions as basis for tumor response assessment on cemiplimab treatment. Additionally, PFS2 will be evaluated based on initial start of IMP.

These exploratory efficacy analyses will be performed using the subsequent cemiplimab monotherapy on progression set.

Objective Response Rate based on PCWG3 and iRECIST (central reading)

ORR will be analyzed separately for PCWG3 and iRECIST (central reading).

The ORR is defined as the number of patients with CR or PR as best objective response per PCWG3 (or number of patients with iCR or iPR as best objective response per iRECIST (central reading)) after start of cemiplimab treatment, divided by the number of patients in the subsequent cemiplimab monotherapy on progression set.

Patients not meeting the criteria for CR or PR (iCR or iPR per iRECIST (central reading)), including those without any post-baseline response assessments, will be considered as non-responders. The ORR will be summarized with absolute and relative frequencies along with two-sided 95% Clopper-Pearson CIs.

BOR (all categories) will be summarized with absolute and relative frequencies.

Duration of Response based on PCWG3 or iRECIST (central reading)

DoR will be analyzed separately for PCWG3 and iRECIST (central reading).

The DoR is defined as the time from the date of first radiographic documented OR to the date of first disease progression or death from any cause, whichever occurs first. Only patients who experience a confirmed OR after start of cemiplimab treatment will be analyzed for DoR.

Only death dates reported prior to or at the date of trial discontinuation will be considered in the DoR analysis.

DoR will be analyzed using the Kaplan-Meier method. Kaplan-Meier plots will be generated.

Patients alive and without disease progression at data cut-off date or patients lost to follow-up will be censored at the day of their last response assessment.

Only response assessments prior to or at the start date of the first subsequent anti-cancer therapy will be considered for DoR analysis. PD within 14 days after the start date of the first subsequent anti-cancer therapy will be considered.

DoR based on PCWG3:

OR is defined as CR or PR. Disease progression is defined as tumor response = Progressive Disease (PD)

DoR expressed in months for patients whose objective response was confirmed CR or PR after start of cemiplimab treatment =

(MIN [Date of first documented disease progression (PD) after start of cemiplimab treatment, date of death from any cause] – Date of first documented overall response (CR or PR) + 1) / 30.4375 for events

or

(Date of the last evaluable response assessment after start of cemiplimab treatment – Date of first documented overall response (CR or PR) + 1) / 30.4375 in case of censoring.

DoR based on iRECIST (central reading):

OR is defined as iCR or iPR. Disease progression is defined as tumor response = Confirmed progressive disease (iCPD)

DoR expressed in months for patients whose objective response was confirmed iCR or iPR after start of cemiplimab treatment =

(MIN [Date of first documented disease progression (iCPD) after start of cemiplimab treatment, date of death from any cause] – Date of first documented overall response (iCR or iPR) + 1) / 30.4375 for events

or

(Date of the last evaluable response assessment after start of cemiplimab treatment – Date of first documented overall response (iCR or iPR) + 1) / 30.4375 in case of censoring.

Progression-free survival based on PCWG3 or iRECIST (central reading)

PFS will be analyzed separately for PCWG3 and iRECIST (central reading).

PFS is defined as the time from the date of the first dose of cemiplimab treatment to the date of the first disease progression, or death from any cause, whichever occurs first.

Only death dates reported prior to or at the date of trial discontinuation will be considered in the PFS analysis.

PFS will be analyzed using the Kaplan-Meier method. Kaplan-Meier plots will be generated.

Patients alive and without disease progression after start of cemiplimab treatment at the data cut-off date or patients lost to follow-up will be censored at the day of their last response assessment.

Only response assessments prior to or at the start date of the first subsequent anti-cancer therapy will be considered for PFS analysis. PD within 14 days after the start date of the first subsequent anti-cancer therapy will be considered.

If no post-baseline response assessment after start of cemiplimab treatment is available, the patient will be censored at the date of the first dose of cemiplimab treatment.

PFS expressed in months = (MIN [Date of first disease progression after start of cemiplimab treatment, Date of death from any cause] – date of first dose of cemiplimab treatment + 1) / 30.4375 if the patient has a PFS event

or

(Date of last evaluable response assessment after start of cemiplimab treatment – date of first dose of cemiplimab treatment + 1) / 30.375 in case of censoring.

Progression-free survival 2 (PFS2) based on PCWG3

PFS2 is defined as the time from the date of the first IMP to the date of the first disease progression after start of cemiplimab per PCWG3, or death from any cause, whichever occurs first.

Only death dates reported prior to or at the date of trial discontinuation will be considered in the PFS2 analysis.

PFS2 will be analyzed using the Kaplan-Meier method. Kaplan-Meier plots will be generated.

Patients alive and without disease progression after start of the first IMP at the data cut-off date or patients lost to follow-up will be censored at the day of their last response assessment. Only response assessments prior to or at the start date of the first subsequent anti-cancer therapy will be considered for PFS2 analysis. PD within 14 days after the start date of the first subsequent anti-cancer therapy will be considered.

If no post-baseline response assessment after start of cemiplimab treatment is available, the patient will be censored at the date of the first dose of cemiplimab treatment.

PFS2 expressed in months = (MIN [Date of first disease progression after start of cemiplimab treatment, Date of death from any cause] – date of first dose IMP + 1) / 30.4375 if the patient has a PFS2 event

or

(Date of last evaluable response assessment after start of cemiplimab treatment – date of first dose of IMP + 1) / 30.375 in case of censoring.

Overall survival for the subset of patients in Arm 1B who are treated with cemiplimab monotherapy

OS is defined as the time from the date of first dose of IMP to the date of death from any cause. OS will be analyzed using the Kaplan-Meier method. Kaplan-Meier plots will be generated. OS expressed in months will be derived as defined in Section 8.7.4.1.

